### **13.2.1 Definition of an Overdose for This Protocol and Reporting of Overdose to the Sponsor and to Merck**

For purposes of this trial, an overdose of pembrolizumab will be defined as any dose of 1,000 mg or greater ( $\geq 5$  times the indicated dose, for a 100 kg patient). No specific information is available on the treatment of overdose of pembrolizumab. Appropriate supportive treatment should be provided if clinically indicated. In the event of overdose, the subject should be observed closely for signs of toxicity.

If an adverse event(s) is associated with (“results from”) the overdose of a Merck product, the adverse event(s) is reported as a serious adverse event, even if no other seriousness criteria are met.

If a dose of Merck’s product meeting the protocol definition of overdose is taken without any associated clinical symptoms or abnormal laboratory results, the overdose is reported as a non-serious Event of Clinical Interest (ECI), using the terminology “accidental or intentional overdose without adverse effect.”

All reports of overdose with and without an adverse event must be reported within 24 hours to the Sponsor and within 2 working days hours to Merck Global Safety. (Attn: Worldwide Product Safety; [contact])

### **13.2.2 Reporting of Pregnancy and Lactation to the Sponsor and to Merck**

Although pregnancy and lactation are not considered adverse events, it is the responsibility of investigators or their designees to report any pregnancy or lactation in a subject (spontaneously reported to them) that occurs during the trial.

Pregnancies and lactations that occur after the consent form is signed but before treatment allocation/randomization must be reported by the investigator if they cause the subject to be excluded from the trial, or are the result of a protocol-specified intervention, including but not limited to washout or discontinuation of usual therapy, diet, placebo treatment or a procedure.

Pregnancies and lactations that occur from the time of treatment allocation/randomization through 120 days following cessation of Merck product, or 30 days following cessation of treatment if the subject initiates new anticancer therapy, whichever is earlier, must be reported by the investigator. All reported pregnancies must be followed to the completion/termination of the pregnancy. Pregnancy outcomes of spontaneous abortion, missed abortion, benign hydatidiform mole, blighted ovum, fetal death, intrauterine death, miscarriage and stillbirth must be reported as serious events (Important Medical Events). If the pregnancy continues to term, the outcome (health of infant) must also be reported.

Such events must be reported within 24 hours to the Sponsor and within 2 working days to Merck Global Safety. (Attn: Worldwide Product Safety; [contact])

### **13.2.3 Immediate Reporting of Adverse Events to the Sponsor and to Merck**

#### **13.2.3.1 Serious Adverse Events**

A serious adverse event is any adverse event occurring at any dose or during any use of a drug product that:

- Results in death;
  - Is life threatening;
  - Results in persistent or significant disability/incapacity;
  - Results in or prolongs an existing inpatient hospitalization;
  - Is a congenital anomaly/birth defect;
  - Is an other important medical event
- 
- **Note:** In addition to the above criteria, adverse events meeting either of the below criteria, although not serious per ICH definition, are reportable to the Merck in the same timeframe as SAEs to meet certain local requirements. Therefore, these events are considered serious by Merck for collection purposes.
    - Is a new cancer (that is not a condition of the study);
    - Is associated with an overdose.

Refer to Table 6 for additional details regarding each of the above criteria.

For the time period beginning when the consent form is signed until treatment allocation/randomization, any serious adverse event, or follow up to a serious adverse event, including death due to any cause other than progression of the cancer under study that occurs to any subject must be reported within 24 hours to the Sponsor and within 2 working days to Merck Global Safety if it causes the subject to be excluded from the trial, or is the result of a protocol-specified intervention, including but not limited to washout or discontinuation of usual therapy, diet, placebo treatment or a procedure.

For the time period beginning at treatment allocation/randomization through 90 days following cessation of treatment, or 30 days following cessation of treatment if the subject initiates new anticancer therapy, whichever is earlier, any serious adverse event, or follow up to a serious adverse event, including death due to any cause other than progression of the cancer under study, whether or not related to the Merck product, must be reported within 24 hours to the Sponsor and within 2 working days to Merck Global Safety.

Additionally, any serious adverse event, considered by an investigator who is a qualified physician to be related to Merck product that is brought to the attention of the investigator at any time following consent through the end of the specified safety follow-up period specified in the paragraph above, or at any time outside of the time period specified in the previous paragraph also must be reported immediately to the Sponsor and to Merck Global Safety.

All subjects with serious adverse events must be followed up for outcome.

**SAE reports and any other relevant safety information are to be forwarded to the Merck Global Safety [contact]**

A copy of all 15 Day Reports and Annual Progress Reports is submitted as required by FDA, European Union (EU), Pharmaceutical and Medical Devices agency (PMDA) or other local regulators. Investigators will cross reference this submission according to local regulations to the Merck Investigational Compound Number (IND, CSA, etc.) at the time of submission. Additionally investigators will submit a copy of these reports to Merck & Co., Inc. (Attn: Worldwide Product Safety; [contact]) at the time of submission to FDA.

**13.2.3.2 Events of Clinical Interest**

Selected non-serious and serious adverse events are also known as Events of Clinical Interest (ECI) and must be reported within 24 hours to the Sponsor and within 2 working days to Merck Global Safety. (Attn: Worldwide Product Safety; [contact]).

For the time period beginning when the consent form is signed until treatment allocation/randomization, any ECI, or follow up to an ECI, that occurs to any subject must be reported within 24 hours to the Sponsor and within 2 working days to Merck Global Safety if it causes the subject to be excluded from the trial, or is the result of a protocol-specified intervention, including but not limited to washout or discontinuation of usual therapy, diet, placebo treatment or a procedure.

For the time period beginning at treatment allocation/randomization through 90 days following cessation of treatment, or 30 days following cessation of treatment if the subject initiates new anticancer therapy, whichever is earlier, any ECI, or follow up to an ECI, whether or not related to Merck product, must be reported within 24 hours to the Sponsor and within 24 hours to Merck Global Safety.

Events of clinical interest for this trial include:

1. an overdose of Merck product, as defined in Section 13.2.1 - Definition of an Overdose for This Protocol and Reporting of Overdose to the Sponsor, that is not associated with clinical symptoms or abnormal laboratory results.
2. an elevated AST or ALT lab value that is greater than or equal to 3X the upper limit of normal and an elevated total bilirubin lab value that is greater than or equal to 2X the upper limit of normal and, at the same time, an alkaline phosphatase lab value that is less than 2X the upper limit of normal, as determined by way of protocol-specified laboratory testing or unscheduled laboratory testing.\*

\*Note: These criteria are based upon available regulatory guidance documents. The purpose of the criteria is to specify a threshold of abnormal hepatic tests that may require an additional evaluation for an underlying etiology.

### **13.2.3.3 Protocol-Specific Exceptions to Serious Adverse Event Reporting**

Efficacy endpoints as outlined in this section will not be reported to Merck as described in Section 13.2.3.- Immediate Reporting of Adverse Events to the Sponsor and to Merck, unless there is evidence suggesting a causal relationship between the drug and the event. Any such event will be submitted to the Sponsor within 24 hours and to Merck Global Safety within 2 working days either by electronic or paper media.

Specifically, the suspected/actual events covered in this exception include any event that is disease progression of the cancer under study.

The Sponsor will monitor unblinded aggregated efficacy endpoint events and safety data to ensure the safety of the subjects in the trial. Any suspected endpoint which upon review is not progression of the cancer under study will be forwarded to Merck Global Safety as a SAE within 2 working days of determination that the event is not progression of the cancer under study

Hospitalization related to convenience (e.g.transportation issues etc.) will not be considered a SAE.

### **13.2.4 Evaluating Adverse Events**

An investigator who is a qualified physician will evaluate all adverse events according to the NCI Common Terminology for Adverse Events (CTCAE), version 4.0. Any adverse event which changes CTCAE grade over the course of a given episode will have each change of grade recorded on the adverse event case report forms/worksheets.

All adverse events regardless of CTCAE grade must also be evaluated for seriousness.

Table 6 Evaluating Adverse Events

Known acute side effects for SRS include: Alopecia within the portal sites, fatigue, headache, nausea, vomiting, worsening baseline neurological deficits due to increased edema or radionecrosis, seizure, skin irritation or redness; Late side effects include radiation necrosis, secondary cancer, seizure, worsening neurological deficit due to edema, death, hair loss within the portal fields.

An investigator who is a qualified physician, will evaluate all adverse events as to:

V4.0 CTCAE Grading	Grade 1	Mild; asymptomatic or mild symptoms; clinical or diagnostic observations only; intervention not indicated.
	Grade 2	Moderate; minimal, local or noninvasive intervention indicated; limiting age-appropriate instrumental ADL.
	Grade 3	Severe or medically significant but not immediately life-threatening; hospitalization or prolongation of hospitalization indicated; disabling; limiting self-care ADL.
	Grade 4	Life threatening consequences; urgent intervention indicated.
	Grade 5	Death related to AE
Seriousness	A serious adverse event is any adverse event occurring at any dose or during any use of investigational product that:	
	† Results in death; or	
	† Is life threatening; or places the subject, in the view of the investigator, at immediate risk of death from the event as it occurred (Note: This does not include an adverse event that, had it occurred in a more severe form, might have caused death.); or	
	† Results in a persistent or significant disability/incapacity (substantial disruption of one’s ability to conduct normal life functions); or	
	† Results in or prolongs an existing inpatient hospitalization (hospitalization is defined as an inpatient admission, regardless of length of stay, even if the hospitalization is a precautionary measure for continued observation. (Note: Hospitalization for an elective procedure to treat a pre-existing condition that has not worsened is not a serious adverse event. A pre-existing condition is a clinical condition that is diagnosed prior to the use of a Merck product and is documented in the patient’s medical history.); or	
	† Is a congenital anomaly/birth defect (in offspring of subject taking the product regardless of time to diagnosis);or	

**Product:** Pembrolizumab (MK-3475, IND 130757)  
**Protocol/Amendment No.:** Rad3179-16 (MK-3475-423), v.5/18/17

	
Is a new cancer (that is not a condition of the study) (although not serious per ICH definition, is reportable to the Sponsor within 24 hours and to Merck within 2 working days to meet certain local requirements); or
 
Is an overdose (whether accidental or intentional). Any adverse event associated with an overdose is considered a serious adverse event for collection purposes. An overdose that is not associated with an adverse event is considered a non-serious event of clinical interest and must be reported within 24 hours to the Sponsor and to Merck within 2 working days..
 
Other important medical events that may not result in death, not be life threatening, or not require hospitalization may be considered a serious adverse event when, based upon appropriate medical judgment, the event may jeopardize the subject and may require medical or surgical intervention to prevent one of the outcomes listed previously (designated above by a †).

Duration	Record the start and stop dates of the adverse event. If less than 1 day, indicate the appropriate length of time and units
Action taken	Did the adverse event cause Merck product to be discontinued?
Relationship to Merck Product	
Did Merck product cause the adverse event? The determination of the likelihood that Merck product caused the adverse event will be provided by an investigator who is a qualified physician. The investigator's signed/dated initials on the source document or worksheet that supports the causality noted on the AE form, ensures that a medically qualified assessment of causality was done. This initialed document must be retained for the required regulatory time frame. The criteria below are intended as reference guidelines to assist the investigator in assessing the likelihood of a relationship between the test drug and the adverse event based upon the available information.
 
The following components are to be used to assess the relationship between Merck product and the AE; the greater the correlation with the components and their respective elements (in number and/or intensity), the more likely Merck product caused the adverse event (AE):

Exposure	Is there evidence that the subject was actually exposed to Merck product such as: reliable history, acceptable compliance assessment (pill count, diary, etc.), expected pharmacologic effect, or measurement of drug/metabolite in bodily specimen?
Time Course	Did the AE follow in a reasonable temporal sequence from administration of Merck product? Is the time of onset of the AE compatible with a drug-induced effect (applies to trials with investigational medicinal product)?
Likely Cause	Is the AE not reasonably explained by another etiology such as underlying disease, other drug(s)/vaccine(s), or other host or environmental factors

### **13.2.5 Sponsor Responsibility for Reporting Adverse Events**

Written IND safety reports will be submitted to the FDA by the IND sponsor, for serious, unexpected suspected adverse reactions within 15 calendar days of learning of its occurrence. If the event is fatal or is deemed to be life threatening, the report will be made within 7 calendar days. The IND sponsor will also make an assessment of whether the event constitutes an unanticipated problem posing risks to subjects or others (UP). This assessment will be provided to the Emory University IRB, which, in turn will make a final determination. If the Emory IRB determines an event is a UP it will notify the appropriate regulatory agencies and institutional officials.

#### **14.1.2 Acute Toxicity, Expansion Cohorts, and Late Toxicity Assessment:**

Once 6 patients are enrolled on any given dose level, there will be a waiting period of 3 months (i.e., at time of second post SRS MRI assessment after pembrolizumab dose (i.e., 3 months after Day 1, cycle 1)); This time point of 3 months and the dose limiting toxicity (i.e. grade 3 RTOG CNS toxicity) is based on similar timeline used on earlier trial to determine the safest radiation dose. Late toxicity (radionecrosis noted on MRI images will also be analyzed at 6 months and at 1 year, but will not be used to stop enrollment on any given dose arm);

During this 3 month waiting period, the MRI images and the patients will be assessed for any signs or symptoms of RTOG CNS toxicity as well as early manifestations of radionecrosis.  $\geq$ Grade 3 CNS toxicity is the only DLT toxicity of principal concern, since the currently used radiation doses are based on this primary endpoint. Patient can still be accrued on other dose arms during this waiting period, while data is being analyzed for safety concerns on a given radiation arm.

Late toxicity (i.e., toxicity starting after 3 months) will also be analyzed. The principal late toxicity of interest is symptomatic radiation necrosis. This is defined as radiographic (typically on MRI) changes consistent with radiation induced necrosis, and the patient also presenting with increased neurological symptoms. Symptomatic radiation necrosis will be recorded at 6 months at at 12 months follow-up;

The radiation dose arm which meets the lowest acute and late toxicity endpoints, but also potentially provided a higher overall systemic response rate, will be considered the best radiation dose level that can be combined with pembrolizumab. Our published series of melanoma patients undergoing SRS alone had an average survival of 38.5% at 1 yr (Patel KR et al, American J. Clinic. Oncology. 2015, May 16. Epub); Our recent multi-institutional review in collaboration with Duke University suggested 1 yr overall survival of 78% for patients undergoing SRS and PD1 in combination (not published, accepted for annual presentation at American Society of Radiation Oncology Meeting, 2016). Thus, we suspect an improvement of 40% in OS compared with SRS alone. With 12 patients on the most immunogenic arm (9Gy x 3), we would be expected to have lowest acute and late toxicity as well as potentially the highest OS benefit and would likely be the arm for a future trial.

With 12 patients per group, a 2-year accrual time with an additional 1 year of follow-up (3 total years), we have 72% power to detect a difference in survival of 40% (78% vs. 38%) at 1 year.

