## 1.0 TRIAL SUMMARY

Abbreviated Title	SRS and Pembrolizumab for Melanoma and Non-Small Cell Lung Cancer (NSCLC) brain metastases (BM).
Trial Phase	Pilot Study
Clinical Indication	Melanoma and NSCLC Brain Metastases
Trial Type	Pilot study with three different radiation dose cohorts.
Type of control	None
Route of administration	Pembrolizumab delivered 200 mg IV every 3 weeks +/- 7 days for at least 2 years, or until progression.
Trial Blinding	N/A
Treatment Groups	All receive pembrolizumab 200 mg IV every 3 weeks +/- 7 days until progression or at least 2 years, with 3 altered radiation dose fractionation groups delivered during first cycle of pembrolizumab.
Number of trial subjects	30 patients.
Estimated enrollment period	2 years
Description of enrollment	
In 2013, we delivered SRS to 20 metastatic melanoma brain metastases patients and 27 NSCLC BM patients. In 2014, we delivered SRS to 14 and 26 patients, respectively. Assuming similar numbers over the next two years, and accruing 45% of patients, we anticipate around 30 patients to enroll.
 
These projected accrual numbers do not reflect the possibility of increased patient referrals from our satellite facilities, and/or increased regional/national referrals, once the trial is opened. We are also not aware of other potentially competing radiation SRS for melanoma and NSCLC brain metastases trials at our institution at this time.

Duration of Intervention	At least 12 months of Pembrolizumab, or until progression.
Duration of Evaluation	3 year ( 2 yrs during accrual, and at least 1 year follow-up for last patient accrued on the study)
Estimated duration of trial	3 years (2 years to accrue + 1 years to follow all patients)
Duration of Participation	3 years
Study Center	Emory University. Atlanta, Georgia.

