### **3.2 Secondary Objective(s), Endpoint(s) & Hypothesis(es)**

#### **3.2.1 Secondary Objectives**

- b. To evaluate intracranial outcomes – control of the treated lesion in the brain with SRS+ pembrolizumab (i.e. local control), development of additional sites of disease in the brain that were not initially treated with SRS (i.e. anywhere intra-cranial failure), intra-cranial progression free survival (local control of the area that received SRS and anywhere intra-cranial failure), extra-cranial disease response (overall progression free survival), rate of leptomeningeal dissemination, and overall survival.
- c. To determine the overall response rate and overall survival of combination SRS and pembrolizumab compared to:
  - i. SRS alone (historical control)
  - ii. Pembrolizumab alone (historical control)
- d. To evaluate treatment response at un-irradiated and extra-cranial sites (i.e. the abscopal effect) with all three arms;
- e. To compare differences in potential immune biomarkers, pretreatment, during treatment, and post treatment;

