### **3.2.4 Secondary Hypotheses**

- a. Using descriptive analyses, combination therapy will result in a higher median survival relative to a historical cohort treated with pembrolizumab alone or SRS alone.
- b. Using descriptive analyses, combination therapy, relative to pembrolizumab alone cohort, will result in higher local control and intracranial control.
- c. Using descriptive analyses, combination therapy, relative to the cohort treated with pembrolizumab alone, will result in a higher improved RECIST and immune RECSIT response rate.
- d. We may see early difference in patients that develop enhanced abscopal response from those that do not, based on early biomarker analysis, and that this could potentially guide future therapy selection.
- e. Radiation necrosis rates may be same, or better with altered dose fractionation compared with single fraction, especially when combined with concurrent PD1;

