#### **4.2.2 Efficacy of Anti-PD-1, Pembrolizumab, in NSCLC Patients**

Building upon the success of pembrolizumab in melanoma, Garon et al. investigated the safety and efficacy of pembrolizumab alone in 495 stage IV non-small cell lung cancer patients. Overall response rate for entire cohort was 19.4%. Current or prior smokers had a higher response rate than never smoker: 22.5% vs. 10.3%. PD-L1 expression on tumors correlated with higher response, as the 23% of patients with a proportion staining score of 50% or higher had a response of 50%. The role of pembrolizumab in combination with SRS for

NSCLC brain metastases has not been evaluated, and is one of an additional area of investigation in our current trial.

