## 5.0 ENROLLMENT CRITERIA

### 5.1.1 Subject Inclusion Criteria

In order to be eligible for participation in this trial, the subject must:

1. Be willing and able to provide written informed consent/assent for the trial.
2. Be  $\geq 18$  years of age on the day of signing informed consent.
3. ECOG PS of 0-1 (See Appendix IV for ECOG definition); Karnofsky Performance Status  $\geq 70\%$ ;
4. Patients must have histological diagnosis of melanoma or non-small cell lung cancer (biopsy will be done per standard of care, if needed to prove metastatic melanoma and/or NSCL as well as for clinically relevant mutation analysis); Additional biopsy will be per standard of care.
5. Patients can be treated either in first line or in the refractory setting; PD-L1 positivity is not required for enrollment;
6. All melanoma patients may be tested for BRAF as part of routine standard of care, but is not a requirement for the trial; All NSCLC patients may be tested for with EGFR and ALK as part of standard of care, but is not a requirement of the trial.
7. Having gotten prior PD1 therapy is allowed for, especially if they have previously progressed on it. Progression may include extra-cranial as well as intra-cranial progression. After progressing on PD1 therapy, intervening chemotherapy and/or targeted therapy (BRAFi, etc) is allowed. If they are on intervening chemotherapy and/or targeted therapy (BRAFi, etc), they have to have progression intra-cranially and/or extra-cranially and must be off intervening therapy for at least 2 weeks.
8. Patient must be asymptomatic at time of getting SRS (day 0) on trial. Prednisone  $\leq 10\text{mg/day}$  for at least 7 days prior to treatment is allowed.
9. Patients with ocular, mucosal and unknown primary melanoma will also be eligible
10. Patients with 1-10 untreated brain metastases at time of initial brain metastases diagnosis (surgery to one of the brain lesions and/or biopsy of a lesion for diagnostic purposes and/or for standard of care purposes is acceptable).
11. Largest brain metastases volume measures less than  $14.15\text{cc}^3$
12. Prior radiation to the primary and/or regional radiotherapy for melanoma and/or NSCLC is acceptable.
13. Baseline labs as within standard of care (CBC, CMP, LDH, ESR, etc) are required within 14 days of enrollment
14. Have measurable disease based on RECIST 1.1.

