### **13.1.1.6 Disease Details and Treatments**

#### **13.1.1.6.1 Disease Details**

The investigator or qualified designee will obtain prior and current details regarding disease status. This includes RTOG RPA class and GPA class, as outlined in APPENDIX II and III.

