#### **14.3.3 Overall Survival**

For overall survival, death from any cause will be defined as the event. Patients will be censored at time of last follow-up. OS will be estimated using the Kaplan-Meier product-limit method.

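### Overall survival in a mixed melanoma and NSCLC cohort is to be read against a melanoma-only SRS-alone figure, with no breakdown by histology or GPA class, so case mix can bias this descriptive comparison in either direction

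*Combined protocol and SAP*

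**What the plan says.** **Population.** Section 5.1.1: "Patients must have histological diagnosis of melanoma or non-small cell lung cancer". There is no quota, and section 6.3 gives stratification as not applicable. Eligibility requires ECOG 0-1 and KPS of at least 70, and allows refractory disease, prior PD-1 therapy and up to 10 brain metastases. On the likely mix, section 1.0 says: "In 2013, we delivered SRS to 20 metastatic melanoma brain metastases patients and 27 NSCLC BM patients". For 2014 it gives 14 and 26.

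**Comparison.** Section 3.2.1, objective c: "To determine the overall response rate and overall survival of combination SRS and pembrolizumab compared to" historical SRS alone and historical pembrolizumab alone. Section 3.2.4(a), which is labelled descriptive, expects that "combination therapy will result in a higher median survival relative to a historical cohort treated with pembrolizumab alone or SRS alone".

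**Benchmarks.** Section 14.1.2: "Our published series of melanoma patients undergoing SRS alone had an average survival of 38.5% at 1 yr". Section 2.3 and the power sentence use 38%. The expected rate with the combination is 78%. No NSCLC figure for SRS alone is given. For pembrolizumab alone, section 4.5.1 puts melanoma response at 26-38%, and section 4.2.2 says of NSCLC: "Overall response rate for entire cohort was 19.4" (per cent).

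**Analysis.** Section 14.3.3: "OS will be estimated using the Kaplan-Meier product-limit method". Section 14.3.2 plans response rates with Clopper-Pearson intervals. Neither mentions histology or prognostic class. Section 13.1.1.6.1 records disease status at baseline: "This includes RTOG RPA class and GPA class". Appendix VI tabulates median survival by histology and GPA class, but section 14 does not use it.

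**The concern.** A historical comparison is only as good as the match between the two groups. Here the benchmark comes from one histology, most of the expected patients have the other, and nothing in the analysis section lets a reader see how far the enrolled patients differ from the reference in prognosis. A pooled 1-year survival above 38% could reflect treatment, a favourable mix, or both. A disappointing figure could equally hide a benefit.

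What is at stake is the reading of objective c and of the 40-point survival gain, which section 14.1.2 supports with a power statement. The wording of hypothesis 3.2.4(a) adds a second difficulty: it is about a median, while the assumed survival is high and follow-up lasts only 12 to 36 months.

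**Working it through.** **1. The plan's own figure.** Section 14.1.2 states 72% power for 78% against 38% at 1 year, with 12 per group, 2 years of accrual and 1 further year of follow-up. Assumed here: exponential survival, uniform accrual, two-sided 5%.

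- Hazard ratio = ln 0.78 / ln 0.38 = 0.257.
- Probability of death by the cut-off: 0.385 and 0.832. Expected events = 12 × (0.385 + 0.832) = 14.6.
- Schoenfeld power = Φ(√(14.6/4) × |ln 0.257| − 1.96) = 73.8%. A simulated log-rank test gives 71.0%.

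The 72% is reproduced, as a comparison of two concurrent groups of 12. The trial has no SRS-alone group, so the comparison relies on the historical figure being a fair stand-in.

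**2. Expected mix.** Melanoma share = (20 + 14)/(20 + 27 + 14 + 26) = 34/87 = 39%, so NSCLC is 61%. In 30 patients this is about 12 and 18.

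**3. One-year survival from case mix alone.** Inputs are the Appendix VI medians. Assuming exponential survival and no drug effect, 1-year survival = 0.5^(12/median). The mix column weights the two histologies 39/61.

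| GPA class | Melanoma median, months | Melanoma 1-year | NSCLC median, months | NSCLC 1-year | Mix |
|---|---|---|---|---|---|
| 0-1 | 3.4 | 8.7% | 3.0 | 6.2% | 7.2% |
| 1.5-2.5 | 4.7 | 17.0% | 6.5 | 27.8% | 23.6% |
| 3 | 8.8 | 38.9% | 11.3 | 47.9% | 44.4% |
| 3.5-4.0 | 13.2 | 53.3% | 14.8 | 57.0% | 55.5% |
| Overall | 6.7 | 28.9% | 7.0 | 30.5% | 29.9% |

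- Overall GPA mix: 29.9 − 38.5 = about −9 points.
- All patients in the best class: 55.5 − 38.5 = +17 points.
- Histology alone, overall: 30.5 − 28.9 = 1.6 points. Within GPA 3 it is 9 points. Moving from the lowest to the highest class changes the mix column by about 48 points.

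**4. Response under pembrolizumab alone.** For the expected mix: 0.39 × 26 + 0.61 × 19.4 = 22.0%, and 0.39 × 38 + 0.61 × 19.4 = 26.7%. This compares with 26-38% for melanoma and 19.4% for NSCLC taken separately.

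**5. Whether the median can be observed.** At 78% 1-year survival the exponential median is 12 × ln 2 / (−ln 0.78) = 33.5 months. With uniform 2-year accrual and a cut-off at 3 years, only patients enrolled in the first 2.5 months can be observed that long, so the expected number at risk is 30 × (2.5/24) × 0.5 = 1.6. In simulation with n = 30, the Kaplan-Meier median is reached in about 48% of trials. If 1-year survival is 70%, it is reached in about 84%; if 60%, in about 98%.

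**The case against.** The strongest reply is that little depends on this. The hypotheses are labelled descriptive, the primary endpoint is CNS toxicity at 3 months, and no stopping or expansion rule uses survival or the 38% figure. Choosing the best arm compares the arms with each other, not with history. All of this stands, and it limits the point to a cheap improvement.

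A reader might also infer more than the documents support:

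- **That case mix could explain the whole claimed gain.** It could not. Even a cohort made up entirely of best-class NSCLC patients reaches only 57% on these medians, well short of 78%.
- **That histology is the main driver.** The overall medians of 6.7 and 7.0 months are nearly equal. Prognostic class matters far more, so a histology split alone would not settle the matter.
- **That the performance-status criteria flatter the trial.** The case mix of the SRS-alone series is not given. The criteria also admit poor prognosis: a melanoma patient with KPS 70-80 and more than 3 brain metastases scores 1 point, the lowest Appendix VI class.
- **That the 38% figure distorts the response comparison.** It is a survival figure only. Pembrolizumab-alone response is given separately by histology, and the plan nowhere adopts the melanoma range as a pooled benchmark. Against that range, NSCLC patients would tend to lower the pooled rate.

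On the median, it is fair to say that the difficulty depends on the 78% assumption, which comes from one unpublished review, and that an unreached median can still be described beside a short historical one. But 78% is the plan's own expectation, and its power sentence is already framed at 1 year.

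**Conclusion.** The point holds as a mismatch in a descriptive secondary comparison. The survival of a cohort expected to be about 61% NSCLC is to be read against a melanoma-only SRS-alone figure, and the planned analyses would not show how case mix contributes. On the protocol's own medians, the shift at the expected histology mix is about −9 points for the overall GPA mix and up to about +17 of the claimed 40 if all patients were in the best class. Its direction cannot be determined from the documents. For response, the issue is only that the pembrolizumab-alone rate differs by histology, with about 22-27% expected for the mix. The median in hypothesis 3.2.4(a) would be reached in about half of trials under the plan's own survival assumption, and more often if survival is lower.

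These sizes assume exponential survival, enrolment in proportion to the 2013-2014 counts, and Appendix VI medians from general brain-metastasis patients. They are illustrations, not forecasts. The primary safety result is not affected.

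**What to change.** - In sections 14.3.2 and 14.3.3, report response and overall survival by histology as well as overall.
- Confine the comparison with the 38% SRS-alone figure to the melanoma subset. Compare response with the pembrolizumab-alone rate of the same histology, noting that the two melanoma trials behind 26-38% excluded brain metastases (section 4.4.1).
- State hypothesis 3.2.4(a) as 1-year overall survival, which the planned minimum follow-up of 1 year supports.
- Tabulate baseline GPA by arm and histology.
- As a labelled sensitivity reference only, give the expected 1-year survival of the enrolled patients from the Appendix VI histology-by-GPA medians. State the exponential assumption, and that these are general brain-metastasis patients and not an SRS-alone cohort.
- Where the documents hold no matching benchmark (NSCLC 1-year survival with SRS alone, NSCLC survival with pembrolizumab alone, any response rate with SRS alone), report the estimate without a comparison.

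The cost is SAP wording and a few tables from data already collected. The price is wider intervals within histology, with about 12 melanoma and 18 NSCLC patients.
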